11.4 Cox modeling approach

Advantages of the Cox modeling approach include (1) automatically includes all follow-up without somewhat tricky choices about the last time point t_0 for cumulative failure time analyses; (2) stable modeling approach in the presence of small numbers of events; (3) we have good *a priori* understanding of how this method should behave; in addition for the calendar-time scale analyses (4) it advantageously accommodates scenarios where the baseline hazard depends strongly and unpredictably on calendar time. Its disadvantages are the usual ones with a strong parametric modeling assumption, including that quantifying uncertainty with a 95% confidence interval about the conditional hazard ratio communicates more precision than we actually have. PH assumptions will be assessed using the Schoenfeld residuals (Grambsch and Therneau, 1994).

11.4.1 Primary analyses

Primary analysis I compares the COVE and CDC-based COVID-19 endpoints among participants randomized to a monovalent or bivalent M6 booster (RM6), counting event starting 13 days post M6 vaccination. To achieve this within a calendar-time-scale Cox regression framework, we consider the following time origin and associated analysis.

Let τ_0 denote the calendar time when the first RM6 participant completed the booster dose. For participant i , the time origin equals the number of days between 13 days after the participant's booster dose and τ_0 . At any calendar time t , the risk set consists of RM6 participants who are at least 14 days post the M6 booster. We consider the following Cox regression model:

$$\lambda_{ji}(t | A_i, W_i) = \lambda_{0j}(t) \exp \{ \beta A_i + \gamma^T W_i \} I(t > \tau_i^{D14}), \quad (4)$$

where $\lambda_{0j}(t)$ is a stratum-j-specific baseline hazard, τ_i^{D14} is Day 14 post M6 booster, $A_i = 1$ if participant i received a bivalent booster and $A_i = 0$ if a monovalent booster. When analyzing data under model (4), we will report $\exp(\beta)$ which measures the hazard ratio conditional on baseline covariates W when comparing bivalent to monovalent M6 booster.

The Cox regression will be conducted using the following stratification and covariate adjustment strategies:

- Stratification: the analysis will be stratified by 4 study groups and the geographic region (RSA or not). Therefore, a total of $4 \times 2 = 8$ strata will be considered.
- Covariate adjustment: the analysis will adjust for sex assigned at birth, history of TB, and a binary indicator of having had an infection during Part A of the study as defined in Section 7.1. The history of TB will not be adjusted in analysis restricting to PLWoH because of the small sample size.

Primary analysis II will be based on the time origin and stratification/covariate adjustment strategies as described above but restricted to the full per-protocol participants (FPP).

Primary analyses III and IV, when applicable, will be based on the same time origin as described above; however, no stratification or covariate adjustment will be conducted because of the expected small number of endpoints.

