• Subgroups IS.Grp1-4	• Groups 1-4 participants in the IS	
• Subgroup IS.PBMC.Imm.Grp1-4	• Groups 1-4 participants in the IS who are also sampled into the PBMC Immunogenicity subset for measuring cellular immunologic markers at Months 0, 1 (Groups 2 and 4 only), 2 (Groups 1 and 3 only), 6, 7 and 12.	
• Subgroup IS.PBMC.Cor.Grp1-2	• Groups 1 and 2 participants in the IS who are also sampled into the PBMC Immune Correlates subset for measuring cellular immunogenicity markers at Months 0, 1 (Group 2 only), 2 (Group 1 only), and 7.	

 SARS-CoV-2 negative is defined by both seronegative and virus detection negative or by seronegative alone if missing virus detection test results.

 SARS-CoV-2 positive is defined by seropositive and/or virus detection positive.

 Major protocol violations are protocol deviations that compromise study integrity; for example, protocol deviations related to collection or reporting of data necessary to interpret the primary efficacy endpoint.

 Immunologic markers measured will include binding antibody and neutralizing antibody markers.

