### 6.3.1 Power calculations for coprimary objectives 1-4 (Efficacy)

Let  $VE(COVID)$  and  $VE(Severe\ COVID)$  denote vaccine efficacy of the vaccine regimen vs. counterfactual placebo among baseline SARS-CoV-2 negative participants against COVID-19 and severe COVID-19, respectively. The relative risk objectives are assessed in terms of cumulative incidence ratios between the active vaccine regimens without analysis of counterfactual placebo arms; the notations  $VE(COVID)$  and  $VE(Severe\ COVID)$  are mainly used for purposes of communicating effect sizes.

The following calculations focus on the COVID-19 endpoint because the severe COVID-19 endpoint could potentially be changed to be a secondary endpoint if there are insufficient severe COVID endpoints (Section 6.4.3). For the assessment of pre-Month 6 stage objectives, sample sizes of Groups 1 and 2 in the FAS are considered. For the assessment of post-Month 6 stage objectives, the following calculations consider approximately 4000 participants in Groups 1-4 received their Month 6 vaccination (mRNA-1273 vs. mRNA-1273.222) per randomization under protocol version 6. This sample size is consistent with study data as of June 2023. As shown in the upper portion (pre-Month 6 stage) of Table 6-2, there is ample power ( $> 90\%$ ) to detect a relative risk of 2.0 between Groups 1 and 2 against the null hypothesis  $H_0: RR = 1.0$  during Month 0 and 6 in the pre-Month 6 stage. In reality, the sample sizes of the PLWH hybrid immunity group who receive 1 pre-Month 6 dose and the PLWH pure vaccine group who receive 2 pre-Month 6 doses are likely smaller than the sample sizes of Groups 1 and 2, respectively. As shown in the lower portion (post-Month 6 stage) of Table 6-2, when the annual incidence of the primary endpoint is in the range of 2.5%- 3.5% in the mRNA-1273 arm, there is approximately 80-90% power to detect a relative risk of 2.0 – 2.5 between mRNA-1273 vs. mRNA-1273.222 vaccination during Month 6.5 and 18 in the post-Month 6 stage.

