These calculations are carried out assuming 5% annual dropout, 5% probability of missing any of the 3 doses, VE(COVID) of 63% between Month 0 and Month 6 in Group 1 (SARs-CoV-2 negative) and in Group 2, and 5% six-month COVID-19 incidence rate among unvaccinated PLWH SARs-CoV-2 negative individuals in the community. The assumption on VE(COVID) of 63% between Month 0 and Month 6 accounts for a possible reduced protection of the vaccine regimen in PLWH against the SARS-CoV-2 variant at the time of the trial conduct. The 5% six-month background incidence rate assumption was based on the observed 4.7%, 5.25%, and 10.38% placebo arm six-month incidence rates among baseline SARS-CoV-2 negative participants in, respectively, the AstraZeneca phase 3 (149), Novavax phase 2 (107), and Janssen ENSEMBLE phase 3 (28) trials restricted to South African study sites, and building in conservative margin given the availability of vaccines to potentially reduce transmission and infection in the region. The background SARS-CoV-2 (re-infection) incidence rate among unvaccinated PLWH SARS-CoV-2 positive individuals in the community is assumed to be half of that of unvaccinated PLWH SARS-CoV-2 negative individuals based on the reported protection of approximately 55% against the Omicron variant from previous SARS-CoV-2 infection in South Africa (150-152) and in other countries (153). The statistical power is calculated using an exact binomial test with a (two-sided) false positive error rate of 0.05.

**Table 6-2 Pre-Month 6 stage:** power to detect relative risk (Months 0-6) being different from 1.0 between Group 1 (n=4200) and Group 2 (n=8400).

True VE (0-6) of Group 1 (n=4200)	Relative Risk (Groups 1 vs. 2)	Total expected number of events M0-6	Power
60%	1.3	189	45%
	1.6	176	85%
	2.0	167	99%
70%	1.2	149	17%
	1.5	135	59%
	2.0	125	96%
70%	1/1.3	207	45%
75%	1/1.6	203	85%
80%	1/2.0	200	99%
75%	1/1.2	159	17%
80%	1/1.5	153	59%
85%	1/2.0	150	96%

**Post-Month 6 stage:** power to detect relative risk (Months 6.5-18) being different from 1.0 between mRNA-1273 vs. mRNA-1273.222 Month 6 vaccination (n=4000, 2000 vs. 2000),.

Annual incidence for mRNA-1273 Month 6 vaccination arm	Relative Risk (mRNA-1273 vs. mRNA-1273.222)	Total expected number of events M6.5-18	Power
3.5%	1.5	110	54%
	2.0	106	93%
3.0%	2.0	91	87%
	2.5	90	99%
2.5%	2.0	76	78%
	2.5	75	96%

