## 6.4 Statistical analyses

This section describes the primary study analysis. Unless otherwise noted, data from enrolled participants will be analyzed according to the initial randomization assignment regardless of how many vaccinations they received.

Analyses for primary endpoints will be performed using SAS and R. All other descriptive and inferential statistical analyses will be performed using SAS, StatXact, or R statistical software.

No formal multiple-comparison adjustments will be employed for multiple safety endpoints or multiple efficacy endpoints. Multiple comparisons adjustment may be performed for secondary endpoints and objectives, which will be specified in the Statistical Analysis Plan (SAP).

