10.1 Cumulative-failure-time-based parameters of interest

Let T be the failure time using the study time scale (based on one of the study time origins defined above), t_0 a fixed time point of interest after the given time origin, and W baseline covariates. For a given analysis, we denote by A a binary indicator of belonging to either of strata which define the comparison groups of interest. In the primary analysis A is indicator of receiving a bivalent or monovalent M6 booster (in analyses), and it is similarly defined elsewhere. We denote by $T(a)$ the counterfactual failure time if $A = a$.

In a cumulative-incidence-based analysis, parameters of interest are the marginalized failure time

Comparing bivalent vs. monovalent booster		
Exploratory analysis I		
Target population	FAS participants receiving a M6 vaccine regardless of randomization scheme (FM6)	
Endpoint	COVE-/CDC-based/Severe (when applicable) COVID-19 endpoints counted 1 day after M6 vaccination	
Time frame	M6 vaccination to M12/M18 visit	
Exploratory analysis II		
Target population	FAS PLWH/PLWoH receiving a M6 vaccine regardless of randomization scheme (FM6)	
Endpoint	COVE-/CDC-based/Severe (when applicable) COVID-19 endpoints counted 1 day after M6 vaccination	
Time frame	M6 vaccination to M12/M18 visit	
Comparing baseline hybrid vs. vaccine immunity among PLWH		
Exploratory analysis III		
Target population	AG1 and AG2.1 receiving a bivalent M6 vaccine regardless of randomization scheme (AG1 and AG2.1 in FM6)	
Endpoint	COVE-/CDC-based/Severe (when applicable) COVID-19 endpoints counted 1 day after enrollment	
Time frame	Enrollment to M12/M18 visit	
Exploratory analysis IV		
Target population	AG1 and AG2.1 receiving a monovalent M6 vaccine regardless of randomization scheme (AG1 and AG2.1 in FM6)	
Endpoint	COVE-/CDC-based/Severe (when applicable) COVID-19 endpoints counted 1 day after enrollment	
Time frame	Enrollment to M12/M18 visit	
Exploratory analysis V		
Target population	AG1 and AG2.1 not receiving M6 vaccination regardless of randomization scheme (AG1 and AG2.1 in FM6)	
Endpoint	COVE-/CDC-based/Severe (when applicable) COVID-19 endpoints counted 1 day after enrollment	
Time frame	Enrollment to M12/M18 visit	
Comparing Month 6 hybrid vs. vaccine immunity among PLWH		
Exploratory analysis VI		
Target population	AG1 and AG2.1 receiving a monovalent M6 vaccine regardless of randomization scheme (AG1 and AG2.1 in FM6)	

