or higher order terms (e.g., splines) unless otherwise specified. In all analyses of groups that were randomized to receive the bivalent or monovalent booster, π is estimated using the sample mean. This is valid because the treatment assignment did not depend on covariates. For other comparisons, we estimate π using logistic regression, and similarly, and we only include linear terms unless otherwise specified.

Nonparametric modeling approach: The conditional probabilities of survival and censoring are estimated using a super learner. For the survival functions η_1 and η_2 , the super learner library consists of the following estimators: (1) Kaplan-Meier estimator; (2) Cox proportional hazard estimator; (3) generalized additive models; (4) survival random forests. In all comparisons of groups that were randomized to receive the bivalent or monovalent booster, π is estimated using the sample mean. Otherwise, the propensity score is estimated using a super learner, with library: (1) the sample average of A – i.e., an intercept-only model; (2) logistic regression model; (3) generalized additive models; (4) random forests. Cross-fitting is performed in order to avoid assumptions that would disallow the use of flexible estimators that do not satisfy complexity (Donsker) conditions.

Due to the low rate of severe COVID-19, no covariate adjustment will be performed for analyses using the severe COVID-19 endpoint.

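### In the RM6 analyses the SAP codes the Month 6 vaccine received but reasons as if it were the vaccine assigned; separately, FPP exclusions carry no time limit

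*SAP*

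**What the plan says.** **Coding of A.** The primary Cox model in SAP 11.4.1 has A equal to 1 "if participant i received a bivalent booster and" 0 for a monovalent booster; the secondary model in SAP 11.4.2 carries the same definition over. For cumulative incidence, SAP 10.1 states: "In the primary analysis A is indicator of receiving a bivalent or monovalent M6 booster". These are the only operational definitions of A for the primary contrast.

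**What A is then taken to be.** Later in SAP 10.1 the same A is a treatment assignment whose randomisation, with Primary analysis I as the example, makes the statistical parameter causal. SAP 10.3 also calls A an assignment. SAP 11.3 estimates the propensity by the sample mean for the randomised comparisons and justifies it so: "This is valid because the treatment assignment did not depend on covariates".

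**Cohorts (SAP 3).** RM6 takes everyone given a Month 6 dose under the randomisation scheme. FPP additionally requires each dose to match assignment and no major protocol violation. The SAP does not define such a violation. Protocol Table 6-1, footnote 3, gives as its example "protocol deviations related to collection or reporting of data necessary to interpret the primary efficacy endpoint", with no time limit.

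**Protocol rule.** Unless noted otherwise, data "will be analyzed according to the initial randomization assignment regardless of how many vaccinations they received" (Protocol 6.4). Protocol 6.2 specifies analysis by actual treatment for the primary safety analyses. It also names the Per-Protocol cohort for post-Month 6 primary efficacy.

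**The concern.** Randomisation protects a comparison of assigned arms. If A records the product given, that protection, the causal reading in SAP 10.1 and the argument for a sample-mean propensity all rest on received and assigned being the same. FPP guarantees this by definition; RM6 does not, and the SAP has no rule for a wrong-product dose. A programmer who follows the model as written would code receipt.

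There was an opening for such errors. SAP 2 says that everyone vaccinated at Month 6 before version 6.0 received monovalent vaccine. The randomisation code was then replaced with treatment numbers kept, and updated keys went to sites. An error could cluster by site or calendar period, and the Cox strata are study group and region, not site.

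The FPP issue is different. Symptom visits and their swabs are triggered by symptoms (Protocol 9.5), so deviations in endpoint data after the dose can arise more often in symptomatic people. Removing people for such deviations makes cohort membership depend on what happened during endpoint counting.

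**Working it through.** **1. Reproduce the plan's power.** Protocol 6.3.1 states: "The statistical power is calculated using an exact binomial test with a (two-sided) false positive error rate of 0.05". Inputs from Table 6-2, post-Month 6 stage: 2000 vs 2000, and the column "Total expected number of events M6.5-18". Given D events, the monovalent share is 0.5 under the null and RR/(1+RR) under the alternative, with 0.025 in each tail.

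| Annual incidence | RR | Events | Stated power | Recomputed |
|---|---|---|---|---|
| 3.5% | 1.5 | 110 | 54% | 54.1% |
| 3.5% | 2.0 | 106 | 93% | 92.9% |
| 3.0% | 2.0 | 91 | 87% | 87.4% |
| 3.0% | 2.5 | 90 | 99% | 98.7% |
| 2.5% | 2.0 | 76 | 78% | 78.1% |
| 2.5% | 2.5 | 75 | 96% | 96.2% |

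The stated powers follow from the stated event counts, so the same test can price the change.

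**2. What coding by assignment costs.** The documents give no count of wrong-product doses; c, the fraction in each arm given the other product, is an assumption. With monovalent risk 1 and bivalent risk 0.5,

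RR(c) = [(1−c)×1 + c×0.5] / [(1−c)×0.5 + c×1].

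Numerator and denominator always sum to 1.5, so total events do not change. At c = 1%: 0.995/0.505 = 1.97.

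| c in each arm | RR by assignment | Power, 106 events |
|---|---|---|
| 0 | 2.00 | 92.9% |
| 0.5% | 1.98 | 92.3% |
| 1% | 1.97 | 91.8% |
| 2% | 1.94 | 90.6% |
| 5% | 1.86 | 86.4% |

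With 91 events, power goes from 87.4% to 85.9% at 1% and 79.0% at 5%. With 76 events it goes from 78.1% to 76.2% and 67.9%.

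**3. When coding by receipt is biased.** Take a true null with mean risk 1 in each assigned arm. Let fraction m₁ of the bivalent-assigned, at relative risk h₁, receive monovalent, and fraction m₂ of the monovalent-assigned, at relative risk h₂, receive bivalent. The as-received bivalent risk is (1 − m₁h₁ + m₂h₂)/(1 − m₁ + m₂); the monovalent one is (1 + m₁h₁ − m₂h₂)/(1 + m₁ − m₂). Both equal 1 exactly when m₁(h₁−1) = m₂(h₂−1).

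- Errors unrelated to risk (h₁ = h₂ = 1): ratio 1.00.
- Equal rates and equal risk in both directions: ratio 1.00.
- One direction only (m₂ = 0), ratio bivalent to monovalent:
  - m₁ = 1%: h₁ = 2 gives (0.98/0.99)/(1.02/1.01) = 0.98; h₁ = 0.5 gives 1.01.
  - m₁ = 5%: h₁ = 2 gives (0.90/0.95)/(1.10/1.05) = 0.90; h₁ = 0.5 gives 1.05.

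The 0.90 end needs 5% × 2000 = 100 bivalent-assigned people wrongly dosed, all at double risk. Analysed by assignment, the null stays at 1.00 in every case.

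**4. FPP exclusions.** No exclusion counts are given; these are assumed. Ratios are monovalent to bivalent, as in Table 6-2.

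- Unrelated to arm and outcome: losing 5%, 10% or 20% leaves 101, 95 or 85 events, with power 92.4%, 89.7% or 83.1%.
- Cases lost in equal proportion from both arms: ratio essentially unchanged.
- Cases lost from the monovalent arm only, starting at 71:35 (2.03): losing 5 gives 66/35 = 1.89; losing 10 gives 61/35 = 1.74.
- True null at 53:53, bivalent cases lost only: losing 5 gives 53/48 = 1.10; losing 10 gives 53/43 = 1.23.

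**The case against.** A reader might infer that the protocol guarantees an as-randomised primary comparison and that the SAP departs from it. The documents do not support that. The rule in Protocol 6.4 is a default that yields where noted otherwise. Protocol 6.2 and Table 6-1 assign objectives 3 and 4 to the Per-Protocol cohort, and Protocol 3 words the comparison in terms of vaccine received, or randomised and received. FPP therefore follows the protocol's own named cohort, and RM6 is closer to an as-randomised analysis than that cohort is. The protocol passages do need reconciling with each other.

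It can also be said that the receipt wording is loose rather than a chosen as-treated analysis. SAP 7.1, Table 2 and the opening of 11.4.1 all speak of randomised arms or participants. That is fair, but the definitions of A are what will be programmed.

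It is unsettled whether a wrong-product dose counts as given under the randomisation scheme at all, so such a person might be outside RM6 rather than switching arms. No such dose is reported; the code change shows only that one was possible.

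On FPP, a reader might infer that exclusions would remove cases and almost no non-cases. Both case definitions need a positive NAAT, so someone whose only swab was missed is usually not a counted case. A counted case could still be dropped, for example one found at a monthly swab after a missed symptom swab. Participants were blinded to the Month 6 product (SAP 2), which limits differences between arms; that section does not state blinding of site staff.

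**Conclusion.** The concern stands as an inconsistency in the RM6 analyses: A is defined by receipt but justified as assignment, with no rule for wrong-product doses. It does not reach Primary II or IV, where received equals assigned.

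The size is probably small. If there were no wrong-product doses, the choice changes nothing. At an assumed 1% in each arm, coding by assignment gives RR 1.97 instead of 2.00 and power 91.8% instead of 92.9%. A false signal from coding by receipt needs errors that are risk-related and unbalanced between directions; 0.90 to 1.05 under a null is the span of the one-directional scenario up to 5%, not an expected bias. A reader might conclude that the sample-mean propensity is invalid, or that Primary analysis I is the only randomised comparison affected. The first would require a material mismatch that no document shows. The second is wrong because Primary III and Secondary I to IV also use RM6.

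The FPP point stands in limited form: the violation rule allows exclusions linked to the outcome after counting starts. The ratio moves only if the loss of cases differs by arm, which the documents neither show nor exclude.

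**What to change.** 1. In SAP 10.1 and 11.4.1 to 11.4.2, define A as the randomised Month 6 assignment under the version 6 key for all RM6 analyses. State that wrong-product recipients stay in RM6 in their assigned arm. Keep coding by receipt for FM6 and safety.
2. In the FPP definition (SAP 3), limit exclusions to listed violations that occur before endpoint counting starts, 14 days after the Month 6 dose. Later violations do not remove a participant.
3. Reconcile the default in Protocol 6.4 with Protocol 3, 6.2 and Table 6-1, so that objectives 3 and 4 have one stated rule for arm and cohort.

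The cost is a few sentences; the assignments are already in the treatment table. Any wrong-product recipients slightly dilute the RM6 contrast, by the amounts in the second table of the working. FPP still shows the result in people who received what they were assigned.

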11.4.2 Secondary comparisons

Secondary analyses I and II counts event starting 1 day after the M6 vaccination. To this end, the following Cox regression model will be considered:

$$\lambda_{ji}(t | A_i, W_i) = \lambda_{0j}(t) \exp \{ \beta A_i + \gamma^T W_i \} I(t > \tau_i^{\text{M6}}), \quad (5)$$

where τ_i^{M6} is M6 booster time of a participant i and the other quantities are defined as those described in Section 11.4.1. We will report the parameter $\exp(\beta)$ which measures the hazard ratio conditional on covariates W .

The same stratification and covariate adjustment strategies as described in Section 11.4.1 will be used in secondary analysis I. Secondary analysis II will not be stratified or adjust for baseline covariates because of the small expected number of endpoints.

Secondary analysis III will be subgroup analysis restricted to RM6 participants who live with HIV (PLHW) or without HIV (PLWoH), counting events 13 days post M6 booster. Analysis will be based on the same Cox regression model (4) and use the same stratification strategy. In addition to the sex, TB history, and an indicator of infection during Part A, analysis restricted to PLWH will further adjust for an indicator of CD4+ cell counts (≤ 500 or not) and an indicator of viral load (detected or not).

Secondary analysis IV is analogous to the secondary analysis III. Secondary analysis IV will be based on the Cox regression model (5) and adopt the same stratification and covariate adjustment strategies as for the secondary analysis III.

Finally, secondary analysis V is analogous to the secondary analysis III except that the analysis cohort will be the FPP (as opposed to RM6) PLWH/PLoW.

